**7.3.10 End of Study (EOS)**

The EOS visit will be performed 30 months from day 0, or after establishment of definitive disease progression, whatever occurs earlier (see Section 8.2.4). Study patients who experience disease progression established prior to the next planned visit are required to complete the EOS visit. For the management of patients impacted by the follow-up extension, see Section 3.1.

The following examinations and procedures will be performed:

- Physical examination

- Vital signs
- Clinical laboratory tests
  - Haematology
  - Serum chemistry and clotting parameters
  - Urinalysis
- Tumour serum biomarker tests
- Pregnancy test
- 12-Lead ECG
- EORTC QLQ-C30 and GI.NET21
- Concomitant medications and SSA medications
- Adverse events
- MRI (CT) evidencing radiological tumour progression by RECIST 1.1: native liver and contrast-enhanced liver and 3 regional (pelvis, abdomen, thorax) MRI or CT, baseline method to be adhered to - not to be repeated in case of progression
- 99mTc-MAG3 renal scintigraphy

### 7.3.11 Early Withdrawal Visit

In case of early withdrawal, the EOS visit is to be performed within 28 days after discontinuation. If the visit cannot be completely performed for any reason, the investigator must make every attempt to complete at least all safety-relevant evaluations:

- Physical examination
- Vital signs
- Pregnancy test
- Clinical laboratory tests
  - Haematology
  - Serum chemistry and clotting parameters
  - Urinalysis
- 12-Lead ECG
- Concomitant medications and SSA medications
- Adverse events
- 99mTc-MAG3 renal scintigraphy

The reason for withdrawal must be noted in patient's file, where known.

## 7.4 Post-Study Evaluations

### 7.4.1 All Patients

As this is an oncological study with overall survival and other progression parameters as secondary endpoints, survival information and progression status, as well as further cancer treatments and the development of late toxicities, including renal toxicity and secondary malignancies will be collected from all randomised patients (including drop-outs, non-compliant patients, other), in compliance with local legal regulations for five years after end of study for each patient. The sites will contact their patients at 6-monthly ( $\pm 1$  month) intervals (i.e. at 6, 12, 18, 24, etc. months after EOS/Early withdrawal) and check the survival status and tumour progression of their patients.

For the management of patients impacted by the follow-up extension, see Section 3.1.

### 7.4.2 Lu-edotreotide Therapy for Patients Progressing under Everolimus

Study patients experiencing disease progression under everolimus have to perform EOS visit and terminate study participation. Subsequently, a patient who progressed under everolimus may be offered Lu-edotreotide therapy based on the personal judgement of the Investigator/treating physician, if he/she considers it to be appropriate and beneficial for the individual patient. In these cases, the investigator can request from the sponsor the provision of study drug to individual patients on a "named patient" basis, as a bona fide unsolicited order, formulated in accordance with the specifications of an authorised healthcare professional and for use by an individual patient under his or her direct personal responsibility as a special needs request.

The administration of this individual treatment requires the patient's consent. 99mTc-MAG3 renal scintigraphy should be repeated if it was performed more than six months prior to the start of individual post-study Lu-edotreotide therapy.

## 8 Procedures and Variables

Patients will provide written informed consent before any study-related procedures can be performed (see Section 13.2).

The schedule of assessments is provided in Table 1 and Table 2.

Unless otherwise specified, all examinations and procedures will be performed by the investigator or authorised study personnel. An additional visit can be scheduled at any time if the investigator considers it to be necessary. This applies especially, when there is clinical suspicion of disease progression. In this situation, the investigator will schedule all necessary clinical investigations, irrespective of the study schedule.

Patient-related events and activities, including specific instructions, procedures, concomitant medications, dispensing of study drug, and descriptions of AEs are to be recorded in the appropriate

source documents. Any findings and information resulting from the below described procedures will be recorded in the CRF (see Section 10.1).

## **8.1 Baseline Characteristics**

### **8.1.1 Demographic Characteristics**

The following demographic characteristics will be recorded:

- Date of birth or age, depending on local requirements on data protection
- Weight, height, ethnic origin, gender

### **8.1.2 Medical and Surgical History, Baseline Findings**

Medical/surgical history and medical conditions present before randomisation will be recorded at the screening visits.

Detailed instructions on the differentiation between (i) medical / surgical history and (ii) baseline findings can be found in Section 8.3.1.1.

### **8.1.3 Prior and Concomitant Medication**

Prior and concomitant medication will be recorded at screening and throughout the study, until the End-Of-Study visit (see Section 6).

### **8.1.4 Tumour Histology**

Only patients with histologically proven, metastasised or unresectable, well-differentiated neuroendocrine tumours of gastroenteric or pancreatic origin (GEP-NET) are eligible for this study. In case of GE-NET, clinical evidence of non-functionality needs to be provided. Central histological re-assessment will be made at baseline using tissue specimens from primary diagnosis or, where unavailable, from a current biopsy.

During screening, a histopathology report of the primary tumour and/or a current tissue specimen, specifying the histological diagnosis, needs to be available. A pseudonymised copy of such report(s) will be collected for the TMF by the monitor for each randomised patient.

Histological diagnosis will be centrally verified for consistency with the current WHO classification 5 (Fletcher et al., 2013). For this purpose, paraffin-embedded blocks or suitable slide-mounted tissue samples obtained during previous interventions will be retrieved from the site pathology and sent to the Central Pathology Laboratory (CPL) University of Bern, Institute of Pathology, [name]. [name]. If no prior sample is available, a fresh tumour sample must be obtained to verify diagnosis (inclusion criterion).

The Central Pathology Laboratory will assess:

- Histological entity
- Tumour grade
- Mitoses per high power field (HPF)
- Ki-67 expression
- SSTR expression
- Chromogranin (CgA) immune reactivity

Argyrophilia or hormone expression will not be assessed.

Only patients with a histology of well-differentiated GEP-NET, as confirmed by the CPL will be included in the per protocol analysis.

To avoid that central pathology review capacity delays enrolment of patients, randomisation and start of treatment may be performed, once availability of paraffin-embedded blocks or suitable slide-mounted tissue samples is confirmed at the study site.

In case the results obtained by the CPL cannot confirm the presence of GEP-NET of tumour grade G1 or G2, the corresponding patients may remain in the study, but will be included only in the safety analysis. If in the everolimus arm, it will be at the discretion of the treating physician to offer continued treatment off-label. The treating physician may also offer Lu-edotreotide therapy if he/she considers it to be appropriate and beneficial for the individual patient.

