### 9.3.3 Analysis Sets

#### 9.3.3.1 Full Analysis Set (FAS)

The Full Analysis Set (FAS) will be used for all efficacy analyses and is defined as all patients who are randomised to treatment; patients in this population will be analysed according to the treatment to which they were randomised. All available data for PFS and survival will be collected and analysed for these patients. For FAS patients who have inadequate data post-baseline to assess efficacy according to the criteria for response or who dropped out before EOS, follow-up will be censored for

analysis of PFS on the date of the last adequate tumour assessment prior to withdrawal (see the Statistical Analysis Plan [SAP] for more details).

The confirmatory analysis of the primary and the 2 key secondary endpoints will be based on the FAS.

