assessment showing progression if in between scheduled assessments; events instead of censoring after two consecutive missed radiological assessments, etc.)

- Drop-out pattern influence on study results, including patient's End of Study at 30 months (from Protocol version 4.0 onwards, including re-consenting) vs. 24 months (before version 4.0, not re-consenting)
- Discrepancies in screening/eligibility status (prior to randomisation) between local and central assessments

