5.2 Analysis Populations

5.2.1 Full Analysis Population (Full Analysis Set)

The Full Analysis Set (FAS) set will be used for all efficacy analyses and is defined as all patients who are randomised to treatment. Patients in this population will be analysed according to the treatment to which they were randomised. All available data for PFS and survival will be collected and analysed for these patients. FAS patients who have inadequate data post-baseline to assess efficacy according to the criteria for response or who dropped out before 30 months follow up (without appropriate PD or death event) will be considered censored for analysis of PFS on the date of the last adequate tumour assessment prior to withdrawal (See Section 3.4.1 for more details).

The confirmatory analysis of the primary and the 2 key secondary endpoints will be based on the FAS.

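### Protocol 8.1.4 puts patients without central G1/G2 confirmation in the safety analysis only, which contradicts the all-randomised FAS that both statistical sections use for the confirmatory tests

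*Protocol*

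**What the plan says.** Three statements in Protocol 8.1.4 matter here.

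- Central review need not come first: "randomisation and start of treatment may be performed, once availability of paraffin-embedded blocks or suitable slide-mounted tissue samples is confirmed at the study site".
- For the per-protocol set: "Only patients with a histology of well-differentiated GEP-NET, as confirmed by the CPL will be included in the per protocol analysis".
- For patients in whom the central laboratory cannot confirm a GEP-NET of grade G1 or G2: "the corresponding patients may remain in the study, but will be included only in the safety analysis".

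The statistical sections say otherwise. In Protocol 9.3.3.1 the FAS "will be used for all efficacy analyses and is defined as all patients who are randomised to treatment", and "The confirmatory analysis of the primary and the 2 key secondary endpoints will be based on the FAS". SAP 5.2.1 repeats both statements; its FAS "set will be used for all efficacy analyses and is defined as all patients who are randomised to treatment". Neither section makes an exception for histology.

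SAP 3.4.1 lists, among PFS sensitivity analyses that could be run, "Discrepancies in screening/eligibility status (prior to randomisation) between local and central assessments". The per-protocol exclusions in Protocol 9.3.3.2 and SAP 6.2 concern dosing and do not name central pathology.

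**The concern.** A randomised patient whose G1/G2 status is not confirmed centrally is in the PFS, ORR and OS tests under Protocol 9.3.3.1 and SAP 5.2.1, and out of all three under Protocol 8.1.4. No sentence says which rule prevails.

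Following 8.1.4 would remove randomised patients from the confirmatory comparison because of a central result that may arrive after randomisation, which departs from the analysis by randomised arm that the FAS requires. It could also reach beyond the final test. The PFS looks in SAP 5.7 are set by event counts (90, 135 and 180), and the ORR boundary depends on the number of evaluable patients out of 300. A programmer working from 8.1.4 and one working from SAP 5.2.1 could therefore arrive at different event counts and boundaries from the same data.

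**Working it through.** **1. The rules side by side, for a randomised patient without central G1/G2 confirmation**

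| Source | Confirmatory PFS, ORR, OS | Per-protocol | Safety (if treated) |
|---|---|---|---|
| Protocol 8.1.4 | out | out | in |
| Protocol 9.3.3.1 and 9.3.3.2 | in | not named as an exclusion | not addressed there |
| SAP 5.2.1 and 6.2 | in | not named as an exclusion | not addressed there |

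The safety-only sentence cannot be read as meaning merely outside the per-protocol set, because 8.1.4 has a separate sentence for that set.

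**2. The plan's own power figure**

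Inputs from SAP 4: 180 events, HR 0.6471 (11/17 months), 2:1 allocation, two-sided 5%, stated power 80%.

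Schoenfeld: power = Φ(√(d × p(1−p)) × |ln HR| − 1.960), with p = 1/3, so p(1−p) = 2/9.

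- √(180 × 2/9) = √40 = 6.325
- 6.325 × 0.4353 = 2.753
- Φ(2.753 − 1.960) = Φ(0.793) = 78.6%

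This is within two points of 80%. A Lakatos-type calculation with 242 patients and 30 months of follow-up each gives 182 events and 81.5% power. The stated figure is reproduced.

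**3. How many patients and events are involved**

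The unconfirmed share q is not in the documents. I assume 3% to 10%.

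- Patients: 300 × 0.03 = 9, to 300 × 0.10 = 30.
- Events per randomised patient at the final trigger: 180/300 = 0.60.
- Events affected: 9 × 0.60 = 5.4, to 30 × 0.60 = 18.

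This supposes that unconfirmed patients have events at the same rate, and in the same arm proportions, as the rest.

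**4. Power if 8.1.4 governed and the 180-event trigger still counted the excluded patients**

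| Assumed q | Patients left of 300 | Events left of 180 | Schoenfeld power |
|---|---|---|---|
| 0 (FAS governs) | 300 | 180 | 78.6% |
| 3% | 291 | 174.6 | 77.4% |
| 5% | 285 | 171 | 76.5% |
| 10% | 270 | 162 | 74.3% |

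At 10%: √(162 × 2/9) = 6; 6 × 0.4353 = 2.612; Φ(2.612 − 1.960) = 74.3%. Over a wider assumed range, q = 1% gives 78.2% and q = 20% gives 69.2%.

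**5. Room in the sample size**

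- 242/0.85 = 284.7, so 285 patients cover the 15% dropout. The plan has 300.
- 300 × 0.85 = 255. Both losses are covered while 255(1 − q) ≥ 242, that is up to q = 1 − 242/255 = 5.1%.

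**6. The condition on step 4**

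If only events in the reduced set counted towards 180, the trigger would come later and little power need be lost, unless the SAP 5.7 fallback (all patients at end of study) applied first.

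**The case against.** The strongest reply is that the primary population is not in doubt. Both documents name one, the FAS, in matching words, and Protocol 9.3.4 refers the detailed analysis procedures to the SAP. Section 8.1.4 describes tumour histology and mentions neither PFS nor the FAS. A reader might infer from the conflict that the plan sets up two primary PFS populations or leaves the choice open. The documents do not support that: a second population arises only by implication, from one sentence.

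A reader might also fear that the choice could be made once results are known. Protocol 9.3.1 and SAP 6.1 require patients to be allotted to analysis sets before any analysis, and SAP 6.2 has per-protocol exclusions confirmed at blind data review. The criterion is also read from baseline tissue and is not an outcome. These safeguards answer the fear about timing. They do not say which rule is to be applied when the sets are drawn up.

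Nor is the silence of SAP 6.2 a clear omission. Its list is introduced as a minimum, and it relies on a protocol deviation plan that is not among the documents. Still, SAP 5.2.2 defines the per-protocol set by serious protocol deviations. Because 8.1.4 permits randomisation before the central result, non-confirmation is not obviously a deviation, so naming it is worthwhile.

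Finally, SAP 3.4.1 already offers a sensitivity analysis on local/central eligibility differences, which presupposes that such patients are in the main analysis. That supports the FAS reading, but the analysis is optional.

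**Conclusion.** The contradiction is real and sits in current text. Protocol 8.1.4 excludes from every efficacy analysis a group of randomised patients whom Protocol 9.3.3.1 and SAP 5.2.1 include in all of them. The statistical sections agree with each other and 8.1.4 is the outlier, so what needs correcting is a stray rule that, if applied, would remove randomised patients from the primary test.

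The size depends on an unconfirmed rate that the documents do not give. At an assumed 3% to 10%, about 5 to 18 of 180 PFS events are affected. A power loss, from 78.6% to between 77.4% and 74.3%, needs two further conditions: that 8.1.4 governs, and that the event trigger counts the excluded patients. If the FAS governs, power is unchanged. A reader should therefore not conclude that the trial as planned is underpowered on this account. The textual conflict is certain; its numerical effect is not.

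**What to change.** 1. Amend the analysis sentence in Protocol 8.1.4: patients without central G1/G2 confirmation remain in the FAS, in the arm to which they were randomised, for all efficacy analyses, and are excluded only from the per-protocol set. The section's text on continued treatment is not part of this point and needs no change for it.
2. Name lack of central confirmation as a per-protocol exclusion in Protocol 9.3.3.2 and SAP 6.2.
3. In SAP 3.4.1, make the optional analysis of local/central eligibility discrepancies a planned PFS sensitivity analysis that excludes these patients.

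The cost is a few sentences across the two documents. No new data are needed, and the sample size, event targets and boundaries stay as they are.

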## **8.2 Efficacy**

### **8.2.1 Tumour Characterisation and Staging**

#### **8.2.1.1 Somatostatin Receptor Imaging (SRI)**

To clinically establish somatostatin receptor (SSTR) expression at baseline, patients undergo somatostatin receptor imaging (SRI) according to local guidelines, preferably with Ga-based PET/CT (e.g. Ga-edotreotide (Ga-DOTATOC) or Ga-DOTATATE). Where Ga-based PET/CT is not available, In-pentetreotide (OctreoScan®) or 99mTc-octreotide SPECT/CT imaging, less preferably planar or SPECT only imaging may be used.

Wherever possible, SRI tomographic hybrid imaging (PET/CT; SPECT/CT), providing three-dimensional information should be performed to alleviate the identification the target lesions, pre-defined per RECIST 1.1. (based on CT/MRI) on the SRI scan. Planar or “SPECT-only-SRI” should only be performed, where tomographic hybrid imaging is not established, as registration/ identification of target lesions with SRI-positive lesions is not easily possible.

All target lesions (up to 5) and ≥90% of non-target lesions need to show adequate tracer uptake, defined as being “clearly differentiable from background” (SSTR positive). This criterion relevant for

eligibility will be assessed by the local investigator. Criteria for SRI scoring are presented in [Appendix 5: Tumour Scoring](#).

Subsequently, image analysis will be centrally verified by the ICL, see Section [8.7](#). Any differences between local and central assessment will be reported.

#### **8.2.1.2 Morphological Imaging (MRI or CT)**

Morphological imaging by MRI / CT will be used a) for the establishment of the radiologically confirmed progressive disease (key inclusion criterion), and b) for the determination of the primary endpoint (PFS).

Two MRI or CT scans obtained using the same method within a maximum of 36 months prior to randomisation, with at least 90 days interval between them, need to demonstrate progressive disease, as per RECIST 1.1. criteria. The most recent scan must not be older than 90 days at randomisation. The minimum interval between two scans must be  $\geq 90$  days.

At baseline, one native liver and contrast-enhanced liver and 3 regional (pelvis, abdomen, thorax) MRI or CT, must be available (performed within 28 days prior to randomisation) or has to be repeated as baseline MRI / CT. Where established, combined imaging (e.g. abdominal MRI / thoracic CT) can be used. The baseline imaging method has to be used consistently throughout the whole study period.

Tumour lesions in the body, and tumour burden in the liver at baseline will be documented, as far as visible on morphological imaging (performed within 28 days prior to randomisation). Tumour burden will be assessed semi-quantitatively/visually. According to RECIST 1.1., a maximum of 5 target lesions, visible on morphological imaging will be defined, in descending order of size. Per organ, only 2 target lesions may be defined. All other lesions are defined as non-target lesions. Only after definition of target lesions on CT / MRI, SSTR expression of target and non-target lesions will be assessed, using SRI (see Section [8.2.1.1](#)).

For follow-up, native liver and contrast-enhanced liver and 3 regional (pelvis, abdomen, thorax) MRIs or CTs will be obtained from all patients in 3-monthly intervals, starting at month 3, until diagnosis of progression or end of study. Additional MRI / CT scans may be performed at any other time if, in the investigator's clinical judgment, progressive disease is suspected. Diagnosis of progression will be made by the local investigator at the point of time when radiological progression criteria, according to RECIST (Eisenhauer et al., 2009) are first met. The RECIST 1.1 and the SRI evaluations performed locally at the study sites will be centrally verified by the ICL (see Section [8.7](#)). For the primary endpoint PFS, the central ICL will perform blinded readings in duplicate, with adjudication in case of discordance will be used.

#### **8.2.1.3 Tumour Markers**

Chromogranin A (CgA) will be determined at baseline, and then monthly until month 12, thereafter in 3-monthly intervals until diagnosis of progression or end of study.

CgA serum concentrations will be considered for the assessment of response to therapy (see Section 8.2.4). In patients with an elevated baseline CgA, changes in CgA serum concentrations could be classified in analogy to published classifications (Bajetta et al., 1993) as follows: Complete biomarker response (CR): return to normal range; partial biomarker response (PR): decrease  $\geq 50\%$  from baseline, biomarker stable disease (SD): An increase by  $< 25\%$  or decrease by  $< 50\%$  from baseline; biomarker progressive disease (PD): increase in CgA by  $\geq 25\%$  from baseline, or compared to prior examination, in patients, where an initial improvement following therapy has been observed.

In addition, specific hormones related to clinical symptoms (e.g. gastrin, insulin, etc.) will be determined in patients, if showing elevated levels at baseline work-up. Response could be graded in analogy to CgA, where merited.

### 8.2.2 Lu-edotreotide Biodistribution and Dosimetry

Biodistribution and dosimetry of Lu-edotreotide will be determined using traditional, current, and innovative methods, in order to comply with regulatory expectations (planar 2D), correspond to the current clinical standard (2D/3D hybrid), and to evaluate innovative dosimetry methods (3D) currently under investigation at leading research institutions. These innovative methods may considerably reduce the effort for acquisition and analysis in the future, thereby greatly facilitating clinical dosimetry.

Dosimetry will be used, a) to determine the AD to kidney, the organ with highest dose exposure in PRRT (safety dosimetry), and b) to determine the AD to tumour lesions, as basis for establishing a dose response relationship, based on the Gy dose achieved in a tumour, rather than based on a Bq dose administered to the patient, as is the current practise. Dosimetry evaluations will be centrally analysed (ICL, see Section 8.7), using a) the MIRD methodology, which is based on a standard phantom to describe the spatial relationship between organs, and b) the Voxel-S methodology, which considers individual activity distribution of the patient, allowing a more precise description of doses to tumours.

